## **A. SPECIFIC AIMS**

Cigarette smoking persists as the leading cause of preventable morbidity and mortality (Centers for Disease Control and Prevention (CDC), 2010). Although there have been many advancements in smoking cessation interventions, the majority of smokers relapse soon after a quit attempt (CDC, 2010; Benowitz, 2009). Despite being more likely to develop a smoking-related disease, females are at a higher risk for smoking relapse compared to males (U.S. Department of Health and Human Services (USDHHS), 2001; Perkins & Scott, 2008). While the specific causal mechanisms associated with the sex difference in relapse rates remain unknown, increasing evidence suggests sex hormones may drive this disparity.

Overall, research to date indicates that estrogen is associated with the facilitation of drug-abuse behaviors, whereas progesterone is associated with reduction of these behaviors (Carroll & Anker, 2010; Lynch & Sofuoglu, 2010). While the clinical literature is mixed, our work offers additional support for this theory as the luteal phase (high progesterone) of the female menstrual cycle appears to be associated with decreased smoking-related symptomatology ([name] et al 2009b) and improved smoking cessation outcomes ([name] et al 2008; [name] et al 2009c) relative to the follicular phase (low progesterone).

Cigarette smokers appear to be more impulsive than non-smokers (Bickel et al 1999), and higher levels of impulsivity are associated with increased risk for smoking relapse (Doran et al 2004). Sex differences have been observed in this association such that females are more susceptible to the effects of impulsivity on smoking (Nieva et al 2011). Preliminary evidence suggests sex hormones may play a role as females who have recently quit smoking have less impulsive behavior while in the luteal phase than in the follicular phase ([name] et al 2009a). Further, within the animal literature, delivery of exogenous progesterone has been shown to decrease impulsive behavior (Llaneza & Frye, 2009).

Taken together, these data suggest that progesterone may improve smoking cessation outcomes perhaps by reducing impulsive behavior. However, the clinical literature on this topic is lacking. Therefore, in Project I we are proposing a double-blind randomized controlled trial to assess the role of exogenous progesterone on impulsivity and smoking cessation in a sample of males and females who are motivated to quit smoking. Subjects (n=200) will be stratified by sex and then randomly assigned to active progesterone (PRO; n=50 males and 50 females) or placebo (PBO; n=50 males and 50 females) to address the following specific aim:

### **Aim 1: Investigate sex differences in the effect of exogenous PRO compared to placebo on impulsivity and smoking cessation**

Hypothesis 1: For both males and females, a lower proportion of subjects randomized to PRO will relapse by 4 weeks after quit date compared to those randomized to PBO.

Hypothesis 2: For both males and females, subjects randomized to PRO will have more days to relapse compared to those randomized to PBO.

Hypothesis 3: There will be a sex difference in smoking relapse such that females, regardless of randomization assignment, will have fewer days to relapse compared to males.

Hypothesis 4: Impulsivity will be a stronger relapse predictor in females than males.

Hypothesis 5: Among those with higher levels of serum PRO the influence of impulsivity on smoking relapse will be dampened.

Given that less than three percent of those who attempt to quit smoking remain abstinent six months later (Benowitz, 2009), there is an urgent need to gain a better understanding of the dynamic process involved in smoking cessation. This project will provide new knowledge regarding the possible protective role of progesterone against smoking relapse in males and females.

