impulsivity, personality characteristics, stress, caffeine use, smoking withdrawal and behavior will be completed. At the second screening visit (Screening Visit 2; scheduled within three days of the first screening visit), baseline impulsivity tasks will be completed. Females will then be provided with urine luteinizing hormone (LH) testing kits with instructions for daily use. The quit date will be set based on LH testing results (details below). The investigators will review the data to determine eligibility. Subjects meeting eligibility criteria will be given instructions on when to come back for their Baseline Visit (details below).

**Quit Date Assignment:** This procedure will be identical to Project II and is described in detail here (Table 1). For *female subjects* the quit date will be assigned during the luteal phase. We have selected the luteal phase (typically the last 14 days of the menstrual cycle; Yee et al 1999) for quit date given that our prior work has demonstrated that this menstrual phase is associated with improved smoking cessation outcomes ([name] et al 2008). Therefore, using identical techniques from our prior work ([name] et al 2008) the quit date will be set as follows: First, to determine date of ovulation, female subjects will use LH tests. Several studies by our group and others have shown that ovulation can accurately be predicted by urine LH testing (e.g. [name] et al 1999, [name] et al 2000, [name] et al 2008, Grinsted et al 1989, Luciano et al 1990). Using the First Response urine testing kit (Carter Products), subjects will determine their LH peak with daily urine testing during specific days of the cycle (See Appendix A for instructions). The testing will be done for ten consecutive days starting on Day 8-12 (depending on cycle length). Although the surge may last up to three days, the first day of the surge is most important, because it predicts ovulation 24-48 hours later. In our prior studies, as well as our current study, subjects found the test easy to use and have been compliant. If no LH surge is identified in the first two months, that female subject will be labeled anovulatory and dropped for ineligibility (estimated < 5% occurrence). Second, once ovulation is detected, the baseline appointment and quit date will be scheduled. The baseline appointment will occur within three days of ovulation. Quit date will be set for seven days after the baseline appointment (i.e. seven to ten days after ovulation).

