(6-14 ng/mL) since that phase has been shown to be favorable for smoking cessation ([name] et al 2008). We expect the following serum progesterone levels by group (Figure 5): (1) females + PRO 9-13 ng/mL; (2) males + PRO 6-7 ng/mL; (3) females + PBO, varies by menstrual phase from 1-14 ng/mL; and (4) males + PBO 0-1 ng/mL (Goletiani et al 2007; Reed et al 2010; Yen et al 1999). Delivery of exogenous progesterone has been successfully used in prior research with a shorter duration of use (i.e. < 1 month) and is generally well tolerated (Sofouglu et al 2001; Sofouglu, et al 2004; Goletaini et al 2007; Reed et al 2010). The most common adverse effect in males and females is sedation. Less common effects include breakthrough bleeding (females), nausea (females and males) and breast tenderness (females) (de Lignieres, 1999; Goletaini et al 2007). While it is possible that progestins may contribute to risk for thromboembolism, we will be using natural micronized progesterone instead of synthetic progestins. Natural micronized progesterone is not known to be associated with thromboembolic risk (PDR, 2002; Goletaini et al 2007), and consequently is a safer choice. Micronized progesterone is not a form of birth control. Therefore, all female subjects will be educated on the importance of using a double-barrier method to protect against pregnancy.

**Adverse Effects:** If a subject is unable to tolerate these side effects of the study medication, those subjects will have the dosage decreased to 200 mg daily. The blind will not be broken to make this determination. [name] will assess the adverse event based on subject self-report of symptoms and advise a dose reduction if needed.

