#### B.4.7. Sample Size & Power Analysis

We expect an approximate drop-out rate of 25% based on our current, more burdensome protocol within a sample of 18-40 year-old females. Therefore, we will enroll a total of 125 female and 125 male participants to ensure we have 100 per sex group to complete the 4 week follow-up for the primary outcome. Participants will be randomized 1:1 to PRO or placebo, separately by sex group, as described above. In our earlier work ([name] et al, 2008), the luteal quit group had a prevalence of 66% relapse at 30 days; this estimates the placebo group relapse rate for our proposed study. Based on a two-tailed Pearson chi-square test with alpha=0.025 for each sex group, a sample size of 100 completers per sex group will have 80% power to detect an odds ratio of 3.5 or higher for comparing smoking relapse prevalence in the placebo group to smoking relapse prevalence in the PRO group. We observed an odds ratio of 3.2 for follicular quit group relapse compared to luteal quit group relapse ([name] et al, 2008). Since our PRO group will receive substantially more progesterone than the typical natural female cycle, it is reasonable to expect a slightly larger odds ratio for PRO compared to placebo. Since the difference in progesterone levels between the male PRO group and the male PBO group will be larger than the difference between the female PRO group and the female PBO group (see Figure 5), we expect a larger odds ratio (hence higher power) for the male treatment comparison.

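### Every woman quits in the luteal phase, so the sex contrast in Hypothesis 3 is confounded with quit phase, and a null or reversed result could not count against a general female disadvantage

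*Combined protocol and SAP*

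**What the plan says.** Hypothesis 3, in Aim 1 and again in DSMP section C, predicts that "females, regardless of randomization assignment, will have fewer days to relapse compared to males". It places no condition on menstrual phase.

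For women, B.4.3 (Quit Date Assignment) states that "the quit date will be assigned during the luteal phase". The reason given is that "our prior work has demonstrated that this menstrual phase is associated with improved smoking cessation outcomes". The quit day falls late in that phase ("i.e. seven to ten days after ovulation"; the DSMP visit description gives seven to nine days). Women with no LH surge in two months are excluded, so only ovulating women enter the comparison. Men are assigned a delay matched to a woman's, which aligns the calendar of procedures and nothing else.

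B.4.7 supplies the size of the phase effect: 66% relapse at 30 days in the earlier luteal-quit group, and "We observed an odds ratio of 3.2 for follicular quit group relapse compared to luteal quit group relapse". B.4.5 gives expected serum progesterone. In the PRO arm it is 9-13 ng/mL for women and 6-7 for men. For women on placebo it "varies by menstrual phase from 1-14 ng/mL; and (4) males + PBO 0-1 ng/mL".

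B.4.8 and DSMP section C address Hypothesis 3 by a sex-by-treatment interaction in an adjusted Cox model. They describe Hypotheses 3 to 5 as not powered and meant to generate hypotheses. B.4.9 (Existing Challenges & Barriers) discusses progesterone delivery, compliance and estrogen, but not the difference in quit timing between the sexes.

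**The concern.** The hypothesis concerns women and men in general. The data will compare men with women whose quit attempt was timed to a phase that the investigators regard as favourable. Quit phase is completely nested in sex, because the trial contains no woman scheduled to quit in the follicular phase. Any sex contrast therefore mixes the effect of sex with the effect of timing, and no model can separate them. Baseline progesterone, a candidate adjuster in B.4.8, does not help: it is measured seven days before the quit date and cannot stand in for a group of women who were never enrolled.

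If luteal quitting helps, the timing pulls the observed contrast towards no female disadvantage. A null or reversed finding could then be taken to undercut the sex difference that motivates the project, when it might reflect only the choice of quit date. The sex comparison is central to the application, and these results are meant to steer later research.

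**Working it through.** **The plan's own figure.** The documents give no power for Hypothesis 3. The related stated figure is 80% power for the primary comparison within each sex (B.4.7: 50 per arm, 66% placebo relapse, odds ratio 3.5, two-sided alpha 0.025).
- Placebo odds = 0.66/0.34 = 1.941. PRO odds = 1.941/3.5 = 0.555, so PRO relapse = 0.555/1.555 = 35.7%.
- Pooled-variance chi-square power at 50 per arm is 79.7%, which reproduces the stated 80%. The 66% and the odds-ratio scale are therefore read as the plan intends.

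**Relapse when quitting in the follicular phase.** Inputs: 66% and odds ratio 3.2, both from B.4.7.
- Odds = 1.941 × 3.2 = 6.212. Relapse = 6.212/7.212 = 86.1%.

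**Women with no phase restriction.** The documents give no phase mix, so the luteal share w is an assumption. Relapse = w × 66% + (1 − w) × 86.1%.

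| Luteal/follicular share | Relapse | Shift from luteal-only (66%) | Female:male odds ratio cancelled |
|---|---|---|---|
| 60/40 | 74.1% | 8.1 points | 1.47 |
| 50/50 | 76.1% | 10.1 points | 1.64 |
| 40/60 | 78.1% | 12.1 points | 1.84 |

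The last column is the odds in the mixed group divided by the luteal odds; for 50/50, (0.7607/0.2393)/1.941 = 1.64. In women on placebo, a true female:male odds ratio of that size would appear as 1.0, and a smaller one would appear reversed. This assumes that the earlier odds ratio carries over in full.

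**Across both arms.** The 66% and 3.2 compare natural phases. Women on PRO take progesterone from seven days before the quit date, so the contrast does not carry over to them directly. If the shift is taken as zero under PRO (an assumption) and half the women are in each arm, the average over all women is 0.5 × 10.1 + 0.5 × 0 = about 5 points (4 to 6 over the same mixes).

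**Duration.** B.4.3 takes the luteal phase as typically 14 days. With the quit date 7 to 10 days after ovulation, 14 − 10 = 4 to 14 − 7 = 7 luteal days remain. Hypothesis 3 concerns days to relapse, followed for 12 weeks. The documents give no phase effect on that scale, so the bias in a hazard ratio over the full follow-up cannot be derived from them.

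**The case against.** The strongest reply is that the bias works against the hypothesis. If women relapse sooner despite favourable timing, the finding is conservative. This stands. A reader might infer that the design cannot support Hypothesis 3 at all, but that is true only of null or reversed results and of the size of any difference.

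A reader might also infer that the trial's premise predicts the opposite of Hypothesis 3, because women are expected to have more progesterone than men. The documents do not support that. They also hold that estrogen facilitates drug-abuse behaviours and that impulsivity affects women more, they call the clinical literature mixed, and they give no separate relapse rate for men. Attenuation follows from the text; reversal does not. The PRO-arm gap (9-13 against 6-7 ng/mL) is a sex difference expected under the same regimen and would exist whatever the quit date, so it is not evidence about quit timing.

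The short luteal window after quitting and the mixed literature make the size uncertain. They do not remove the confounding. The 66% and 3.2 are themselves 30-day results classified by phase at quit, and the investigators rely on them for scheduling and planning.

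Finally, Hypothesis 3 is declared exploratory, the luteal rule is openly described, and nothing in the plan says that a null would be read as evidence against a female disadvantage. This limits the seriousness. It does not remove the mismatch between an unrestricted hypothesis and a restricted comparison.

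**Conclusion.** The point holds as a limit on interpretation. The sex contrast is confounded with quit phase by design, adjustment cannot repair it, and the probable bias is towards no female disadvantage. The direction rests on the plan's own premise that luteal quitting favours cessation.

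The size is about 10 points of 30-day relapse in naturally cycling placebo women, given an even phase mix and full carry-over of the earlier odds ratio. A reader might apply those 10 points to all women or to days to relapse. The documents support neither: across all women the figure is about 5 points if the shift is confined to placebo, and for days to relapse it is unknown.

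A related gap must be closed first. The planned sex-by-treatment interaction asks whether the treatment effect differs by sex. It does not test a sex difference holding in both arms, so the contrast that needs the caveat is not yet specified.

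**What to change.** 1. In Aim 1 and in DSMP section C, restrict Hypothesis 3 to women quitting in the luteal phase compared with men.
2. In B.4.8 and DSMP section C, name the sex main effect in the Cox model as the contrast for Hypothesis 3, in addition to the planned interaction, and report it pooled and by arm. The by-arm display shows where the natural-phase contrast applies; it does not reduce the confounding.
3. In the same two places, state that the contrast applies only to luteal-phase quit dates, that the expected bias is against Hypothesis 3, and that absence of a female disadvantage will not be taken as evidence against one at other quit times.

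The cost is a few sentences, one named model term and one extra table, with no change to visits, participants or quit-date scheduling. The downside is a narrower exploratory claim.

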## **B. RESEARCH STRATEGY**

### **B.1. SIGNIFICANCE**

Cigarette smoking continues to be the number one cause of preventable morbidity and mortality in the United States (CDC, 2010). Compared to males, females are at an increased risk for development and maintenance of nicotine addiction (USDHHS, 2001). Preclinical and clinical studies have offered evidence to explain these observed sex differences, suggesting that sex hormones may modulate the reward system and related nicotine response (Lynch & Sofuoglu, 2010). Specifically, high levels of estrogen are associated with a heightened response to nicotine; whereas, high levels of progesterone are associated with a blunted response (Carroll & Anker, 2010; Lynch & Sofuoglu, 2010). Further, within the animal literature the administration of progesterone has been shown to be associated with reduced reinforcing effects of drugs, as well as a decrease in self-administration and drug-seeking behavior (Carroll & Anker, 2010).

Recent studies suggest that progesterone may play a key role in the observed sex differences in addictive behaviors. A review by Lynch & Sofuoglu (2010) concluded that progesterone (PRO) may counter the enhanced vulnerability in females by altering the biological response to nicotine's reinforcing effects. Other clinical research on smoking cessation by menstrual phase has indicated that the follicular phase (low PRO) may be associated with more favorable outcomes when paired with nicotine replacement therapy (Franklin et al 2007; Carpenter et al 2008); whereas the luteal phase (high PRO) may be associated with more favorable outcomes when either no medication or non-nicotine medications (i.e. bupropion) are used ([name] et al 2008; Mazure et al 2011). However, the specific mechanisms as to how PRO may assist with smoking cessation efforts remain unknown. Given that PRO has been shown to reduce impulsive behaviors in animals (Llaneza and Frye, 2009) one theory is that PRO blunts impulsivity in humans and, therefore, protects against smoking relapse.

Further clinical research has focused on association of various personality traits, primarily impulsivity. Impulsivity has four factors including a lack of premeditation regarding the consequences of behavior, lack of perseverance when tasks are boring or aversive, sensation seeking and urgency, and the tendency to behave impulsively while experiencing negative affect (Doran et al 2009). Sex differences in the association between impulsivity and smoking behavior have been observed. For example, one recent study observed that high levels of impulsivity were associated with increased nicotine use in females, but not males (Stoltenberg et al 2008). A second study observed a positive association between two factors of impulsivity – sensation seeking and general activity – and number of cigarettes smoked per day in females, but not males (Nieva et al 2011). The role of sex hormones in these associations is unclear; however, taken together this offers evidence for a possible interaction between PRO, impulsivity and smoking behavior.

[figure not shown]
This SCOR application proposes robust comparisons of hormonal influences in clinical and preclinical studies. Here, in Project I, we propose direct and additive conditions. Specifically, we will assess the effects of PRO, compared to placebo (PBO), as well as the sex differences on impulsivity and smoking cessation outcomes in females and males who are motivated to quit smoking using a 12-week double-blind randomized clinical trial.

This project, especially in the context of the other projects, is highly significant in several domains. First, the proposed work directly compares female and male subjects with respect to PRO modulation of smoking cessation. Second, because PRO and impulsivity both have a role in smoking cessation and relapse, a direct comparison of PRO versus PBO on impulsivity is important. Third, these data will directly address (a) the role of PRO on smoking cessation outcomes, (b) the role of sex differences on smoking cessation outcomes, (c) the role of impulsivity on smoking cessation outcomes, and (d) interactions of sex, PRO and impulsivity on smoking cessation outcomes. Fourth, while Project I will focus solely on nicotine and PRO effects on nicotine, Project II, using similar design features, will focus on cocaine with co-morbid nicotine use in humans and the combined effects of PRO and atomoxetine. Project III will conduct parallel preclinical studies to both projects. Therefore, the complete data set will provide unique and significant insights into sex differences as well as, translational data. Finally, the combined expertise of the assembled named investigators is unique and greatly enhances the probability that the work will be completed as proposed and that significant findings will be forthcoming.

## B.2. PRELIMINARY STUDIES

[figure not shown]
**B.2.1. Impulsivity Varies by Menstrual Phase after Exposure to Nicotine.** *Goal:* This cross-over study aimed to measure differences in nicotine response between follicular (F) and luteal (L) menstrual phases in a sample (n=20) of female smokers between the ages of 18 and 40. *Results:* After exposure to nicotine nasal spray, subjects in the F phase became significantly more impulsive on the Immediate Memory Task computer program (Doughtery et al 2002) compared to subjects in the L phase (Figure 1). *Relevance:* Sex hormones appear to impact the level of impulsivity, such that high levels of progesterone are associated with less impulsivity after exposure to nicotine. The association between progesterone and impulsivity may be associated with risk for relapse.

Figure 1. Changes in Impulsivity by Menstrual Phase

[figure not shown]
**B.2.2: Smoking Satisfaction & Enjoyment Vary by Menstrual Phase during Ad Libitum Smoking.** *Goal:* The purpose of this cross-sectional study was to investigate the differences in reinforcing effects (mCEQ) of smoking by menstrual phase and depressive symptoms in a sample of female subjects (n=39) who were classified into four groups: no depressive symptoms follicular phase (NDS-F), no depressive symptoms luteal phase (NDS-L), depressive symptoms follicular phase (DS-F) and depressive symptoms luteal phase (DS-L). *Results:* Smoking Satisfaction varied by menstrual phase in the NDS group but not the SDS group (F-NDS: 5.2±0.5; L-NDS: 3.4±0.5; F-SDS: 4.5±0.4; L-SDS: 4.8±0.3; p=0.016; Figure 2) and a similar trend was observed within the Enjoyment subscale (F-NDS: 4.4±0.6; L-NDS: 1.7±0.6; F-SDS: 3.6±0.5; L-SDS: 2.9±0.5; p=0.089). *Relevance:* Among those without depressive symptoms, sex hormones appear to impact the level of reinforcing effects of smoking, such that high levels of progesterone are associated with less smoking satisfaction and less enjoyment.

Figure 2. Smoking Satisfaction Subscale by Depressive Status and Menstrual Phase

**B.2.3. Pharmacokinetics of Nicotine varies by Menstrual Phase in Women without Depressive Symptoms.** *Goal:* This cross-over study aimed to measure menstrual phase differences in pharmacokinetics after exposure to nicotine nasal spray within a sample of abstinent female smokers with regular menstrual cycles who either had depressive symptoms (n=23) or did not (n=24). *Results:* There was a significant interaction between depressive symptoms status and menstrual phase such that those without depressive symptoms had a significant menstrual phase difference in their maximum nicotine concentration levels (p=0.020; Figure 3). *Relevance:* In women without depressive symptoms high

Figure 3. Mean Plasma Nicotine Concentrations Following Nicotine Nasal Spray Use

progesterone levels are associated with lower nicotine response; this may be associated with risk for relapse.

**B.2.4. Changes in Estradiol/Progesterone (E2/P) Ratio are Associated with Changes in Craving. Goal:** This cross-over study aimed to assess the influence of the E2/P ratio on smoking-related symptoms of withdrawal (MNWS), smoking urges (Brief-QSU), and reinforcing effects of smoking (mCEQ) using a within subject analysis in a sample of female smokers (n=50) with regular menstrual cycles between the ages of 18 and 40. **Results:** During ad libitum smoking, an increase in the E2/P ratio was associated with an increase in craving on two independent items of measurement: mCEQ ( $t=2.38$ ,  $p=0.02$ ) and MNWS ( $t=1.92$ ,  $p=0.06$ ). **Relevance:** Changes in sex hormone levels are associated with changes in craving for cigarettes.

